The James R. Clark Sickle Cell Memorial Foundation (SC Memorial Foundation) is not engaged in this research. The Foundation will serve as a community-based, recruitment site through which potential participants will be contacted and informed about the study. Emory study staff will coordinate, in person or remotely, recruitment and participant onboarding activities for potential participants identified through the SC Memorial Foundation.

The participant burden is estimated to be 45 minutes at each time point for surveys, 2 hours weekly of intervention for 8 weeks, and 1 hour for qualitative sessions. Participants will receive \$50 after baseline, \$50 after each 4-week study period (\$150 in total), and \$50 after the qualitative sessions.

14. Withdrawal of Participants

Data collection will be monitored daily by the study team. Participants will be sent a reminder text or email if they do not submit data after 4 days. If no response is received after 2 days, a team member will conduct a telephone call. We will use a maximum of 3 attempts to contact participants. If 2 weeks have passed since last data submission and contact attempts have been unsuccessful, the participant will be considered lost to follow-up and will be withdrawn from the study. Before making this determination, we will try to regain contact with the participant (via 3 telephone calls and, if necessary, a certified letter mailed to the participant's last known address). These attempts will be documented in the participant's study file.

We may conclude an individual's participation in this study without their consent for any reason, especially if we believe it is in their best interest or if they were to object to any future changes that may be made in the study plan. Expected reasons for conclusion of participation may include:

- Experiencing any symptoms of cybersickness or digital motion sickness (such as dizziness, lightheadedness, issues with balance, nausea, and/or vomiting) during or after exposure to VR
- Experiencing severe mental distress

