If participants do not finish any portion of the study, then they will be compensated for the portion(s) they have completed and will no longer have their data collected after they have withdrawn from the study. Data that were already collected may still be used for this study as we try to understand pain in individuals with sickle cell and develop interventions. If participants would like us to discontinue use of their data after they withdraw from the study, then they will contact the principal investigator, at

the mailing address provided, with a written request. Once we receive the written request, their data will be destroyed.

15. Risks to Participants

Potential Risks

This study involves minimal risk, if any. Exposure to VR may result in an infrequent physical risk of cybersickness or digital motion sickness. In addition, we will solicit information regarding participants' pain and disease experiences. Therefore, there is a potential, likely, infrequent psychological risk because discussion of these experiences might result in emotional distress and/or embarrassment to the participants. There may also be rare, social risks in that there may be social harm (i.e., stigmatization) to the participant and larger community of individuals with SCD. A breach of confidentiality may result in social consequences such as being perceived negatively by healthcare providers, family members, or employers. Economic consequences may also arise if individuals need to choose an alternate healthcare provider because of a breach of confidentiality. This alternate healthcare provider may be in another county or state. Accordingly, the participant may incur costs for transportation and/or care.

Procedures to Reduce Risks

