Study recruitment and data collection will occur in person, in a private area of the SCD clinic, SC Foundation, or research center, or remotely while participants are at home. All potential participants will be screened for eligibility using the inclusion and exclusion criteria. Eligible participants will receive information about the study, and will be asked to complete an informed consent, or a verbal informed consent, and a Health Insurance Portable and Accountability Act (HIPAA) authorization form. The informed consent document states that participants may choose to not answer any question or may end their participation in the study at any time. During the interviews or focus group sessions, participants will be reminded that their participation is voluntary and that they may stop at any time if they are uncomfortable with any questions.

Prior to treatment, we will ask potential participants screening questions, using the Questionnaire to Screen for Cybersickness or Digital Motion Sickness, to determine whether they have had or may have any of these issues. If so, they will not be considered eligible for participating in the VR group only. If they are considered eligible for the VR group (provided no affirmative responses to the screening questions), then participants will remotely complete the Virtual Reality Sickness Questionnaire before each use of the VR program. Only individuals without severe symptoms, as reflected on the questionnaire, will move forward with VR use. These individuals will also be asked to remotely complete the Virtual Reality Sickness Questionnaire after each use of the VR program. Participants who are randomized to the VR group will be instructed to adhere to the usage recommendations specified by the VR program's manufacturer. In addition, VR participants will be instructed not to use the VR device while ambulating, and that they should use the headset a maximum of 3 times per 24-hour period (morning, noon, and evening) for not more than 30 minutes consecutively. During the 8-week, home VR

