use period, we will use telephone calls or text messages to conduct weekly study assessments of adverse events. Users of the VR program who experience adverse events are free to suspend or halt VR use at any time by removing the headset. This can remedy the VR side effects. In addition, the VR program offers a range of experiences to allow participants to identify lower risk experiences. For participants who experience adverse events, we will discontinue their study participation and refer them to a member of the medical team as needed for any medical follow-up. All participants will have the ability to withdraw from the study at any time.

At this time, the risks of VR during pregnancy (i.e., risks to the pregnant woman, the embryo, or fetus) are not yet known. Therefore, to protect against possible side effects, women who are pregnant or nursing a child will not participate in exposure to VR. Female participants will be asked to immediately notify study staff if they become pregnant during the study. In that case, they will not be exposed to VR but may continue with other remaining study activities.

Active suicidal ideation, as documented in the patient's medical records, is one of the exclusion criteria. Among eligible participants, we will assess depression with the PROMIS® Emotional Distress – Depression (Short Form) at baseline, mid-treatment, and monthly post-treatment via remote data collection. This measure does not include a suicide item. To manage participants who score in the upper range of the depression measure or disclose suicidal ideation, we will utilize the following protocol.

- a. At the end of the survey in the questionnaire management system, participants will see this statement: *If you are feeling distressed or you are having thoughts of hurting yourself, please call 911, call the 24-hour Georgia Crisis and Access Line at [name], call the South Carolina 24-hour Crisis Response Dispatcher at [name], go to Grady Memorial Hospital or your local hospital, or call your healthcare provider.*

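### The adverse-event rule ends study participation and outcome collection, not only treatment; where it is applied to cybersickness, later outcomes are lost for a reason that cannot arise in the audio arm

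*Combined protocol and SAP*

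**What the plan says.** Section 15 (Risks to Participants, Procedures to Reduce Risks) states: "For participants who experience adverse events, we will discontinue their study participation". It gives no threshold for severity or relatedness, and its wording is not limited to one arm.

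Section 14 (Withdrawal of Participants) says that people who do not finish "will no longer have their data collected after they have withdrawn from the study". It adds: "Data that were already collected may still be used for this study", unless the participant asks in writing to have the data destroyed.

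Section 14 also gives the study team discretion to end participation. Its list opens with "Expected reasons for conclusion of participation may include" and contains two items. One is "Experiencing any symptoms of cybersickness or digital motion sickness", tied to symptoms "during or after exposure to VR". The other is "Experiencing severe mental distress", which either arm could meet.

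Other parts of Section 15 are milder. On the sickness questionnaire completed before each session: "Only individuals without severe symptoms, as reflected on the questionnaire, will move forward with VR use". VR users may also pause or stop the headset themselves, or pick experiences with lower risk.

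Controls receive audio only (Sections 5 and 6). Section 18 (Data Analysis) promises intent-to-treat procedures, REML mixed models, a review of attrition by participant characteristics, and a missing-data sensitivity analysis with no method named. Model estimates by arm and time point are to supply effect sizes for future studies.

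**The concern.** An intent-to-treat comparison needs outcomes from everyone randomised, including those who stop treatment. Read together, the adverse-event sentence in Section 15 and the stop on data collection in Section 14 turn a treatment stop into a loss of outcomes. For cybersickness the loss is related to treatment and confined to one arm, because the trigger needs VR exposure.

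Two products of the pilot are exposed. The first is the between-arm effect-size estimate, including the one for pain catastrophizing, the primary measure in Section 4. The second is the retention and non-completion rate, a feasibility parameter in the same section: a removal rule creates non-completion in the VR arm that says nothing about willingness to stay. Loss is already heavy. The Revision History reports observed non-completion at more than double the assumed 20%.

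**Working it through.** **1. The plan's own figure.** The Revision History gives 40 participants, a detectable difference of 0.9 SD, 80% power and a 5% level. With 1:1 allocation and a two-sided test, n per arm = 2 × (1.960 + 0.842)² / 0.9² = 19.4, so 20 per arm and 40 in all. Power at 20 per arm is 81.2% by the normal approximation and 79.2% by the noncentral t. The figure reproduces. Enrolling 70–90 to finish with 40 implies total loss of 1 − 40/70 = 43% to 1 − 40/90 = 56%, from all causes.

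**2. The rules side by side.**

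| Event | Treatment | Participation and data | Place |
|---|---|---|---|
| Adverse event | not treated separately | discontinued (*will*); collection then stops | Sections 15 and 14 |
| Any cybersickness symptom with VR | not treated separately | may be ended | Section 14 |
| Severe symptoms before a session | no VR use | not mentioned | Section 15 |
| Pregnancy | no VR | other activities may continue | Section 15 |
| Severe depression score or suicidal ideation | not stated | participant may choose to continue | Section 15 |

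The protocol therefore already separates stopping VR from leaving the study for pregnancy, and lets participants with serious mental-health findings remain. It gives no reason for treating adverse events differently.

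**3. What remains of a removed participant's data.** In Table 1 (Section 6), pain catastrophizing is measured at baseline and at weeks 4, 8 and 12. Someone removed before week 4 contributes a baseline score only. The pain outcome fares better, because the diary is daily through day 56.

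**4. Illustration of size. Every input is an assumption.**

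- Share of the VR arm removed, q: 5–24%. The upper value is the complement of the 76% without nausea or motion sickness in the earlier EaseVRx trial cited in Section 3 (100 − 76 = 24). It counts symptoms in other pain conditions, not removals. The lower value is chosen because this trial screens out susceptible people and calls the risk infrequent.
- Difference between removed and retained, δ: 0.5–1.0 SD, in either direction.
- VR arm if all 70–90 are randomised 1:1: 35–45. Removed: 0.05 × 35 = 1.75 to 0.24 × 45 = 10.8, so about 2–11 people. Section 5 plans headsets for about 25 users, which would give 0.05 × 25 = 1.25 to 0.24 × 25 = 6, but 25 does not fit an enrolment of 70–90.

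If the removed differ from the retained by δ, the full-arm mean differs from the retained mean by q × δ:

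- low: 0.05 × 0.5 = 0.025 SD
- high: 0.24 × 1.0 = 0.24 SD

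The sign follows the assumed direction. For scale, the 95% half-width of a two-sample comparison with 20 per arm is t(0.975, 38) × √(2/20) = 0.640 SD, so the shift is 4% to 37% of it.

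**5. What the mixed model can recover.** Suppose week 4 scores are kept and already show the difference, baseline scores do not, and visits are equally correlated at ρ. The model recovers a fraction ρ/(1 + ρ) of the shift: 0.333 at ρ = 0.5 and 0.412 at ρ = 0.7. The remaining shift is 0.015–0.017 SD at the low end (0.025 × 0.588 to 0.025 × 0.667) and 0.14–0.16 SD at the high end (0.24 × 0.588 to 0.24 × 0.667). With removal before week 4 and no baseline difference, nothing is recovered for pain catastrophizing.

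**The case against.** The strongest reply is that the strict rule may not be the working rule. Ending participation for cybersickness is discretionary in Section 14, only severe symptoms bar a VR session in Section 15, and users may pause or change experiences. The sickness questionnaire before and after every use would have little purpose if one symptom ended participation. This stands: a reader might infer that any symptom must lead to removal, and the documents do not support that. What remains is one unqualified sentence saying *will*, in conflict with the text around it, and no provision for outcome surveys once someone is removed.

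Section 6 says data will be collected whenever possible. That concerns participants unable to complete activities; it does not override the specific stop on collection after withdrawal in Section 14.

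REML is valid if missingness depends only on observed data, so the comparison is not void, although a reader might infer that it is. But the model cannot replace outcomes that the protocol chooses not to collect, and early removals leave it little to work with on the primary measure.

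The arm sizes are also uncertain. People who screen positive for cybersickness are ineligible for the VR group only, so arms of 35–45 need not result.

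Finally, this is an exploratory pilot with 43–56% loss from all causes, and the share due to this rule is unknown. That limits the claim but does not remove it, because estimating effect sizes is the pilot's stated purpose.

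**Conclusion.** The point holds in a limited form and should be fixed. As far as the mandatory sentence in Section 15 is applied, VR participants with cybersickness lose later outcomes for a treatment-related reason that cannot arise with audio. That weakens the intent-to-treat comparison and the effect-size and retention estimates. The planned safeguards mitigate this only in part.

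The size is not known. Under the assumed 5–24% removal and 0.5–1.0 SD difference, the completer comparison shifts by 0.025–0.24 SD. The low end is negligible, and the high end needs both extremes at once.

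Two stronger conclusions are tempting. A reader might infer that the rule flatters VR; nothing in the documents says whether those with cybersickness would have done worse or better. A reader might also turn the shift into a false-positive rate. That would describe an unadjusted test on completers with assumed inputs, not the planned repeated-measures model, so no such rate is claimed here. Confidence is medium: the text is clear, its application is not.

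**What to change.** Amend Sections 14 and 15 so that:

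- an adverse event or cybersickness stops VR or audio use, not study participation;
- these participants stay on the remote week 4, 8 and 12 surveys and on adverse-event follow-up unless they withdraw consent for data collection, much as Section 15 already allows for pregnancy;
- the stop on data collection in Section 14 applies to withdrawal of that consent;
- *may* in Section 14 and *will* in Section 15 agree, with the symptom threshold for stopping VR left to the investigator as a clinical decision.

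State in Section 18 that these participants are analysed in their assigned arm, except where data are destroyed on written request. A delta-shift analysis in both directions would be one way to specify the sensitivity analysis already promised; it is optional. No new adverse-event recording is needed, because Sections 15 and 19 already cover onset, action taken and causality.

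Cost: an IRB amendment with consent wording, and possible re-consent of current participants, since Version 9 was written after dropout had been observed. This is not costed here. Survey payments are at most $150 per retained person, so 10.8 × $150 = $1,620 at the highest illustrated removal. Surveys are already remote, so no visits are added. Some people who stop treatment will still not respond.

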After screening patients for eligibility using the inclusion and exclusion criteria, the project coordinator will describe the study to and seek participation from eligible individuals. Participants will be informed that the purpose of the study is to test a pain management intervention that will be delivered in two different ways, but their group allocation will not be revealed. The study conditions will be presented as adjuncts to standard care and there will be no restriction on using other pain management methods. After patients provide written, informed consent or verbal informed consent, they will complete baseline study questionnaires. Once enrolled, participants may self-withdraw at any time, or they may be withdrawn if they fail to or are unable to comply with study procedures. In that case, recruitment will resume and continue until the target number of participants is reached.

After completing baseline questionnaires, participants will be randomized 1:1 to receive either EaseVRx or control. Only individuals meeting the eligibility criteria for VR will be assigned to the VR group. Participants will receive study materials and instructions for home use before being followed prospectively for 8-weeks with follow-up at 12 weeks. Participants in the VR group will receive an all-in-one, non-tethered VR headset (Pico G24K headset with AppliedVR breathing amplifier) that is pre-loaded with EaseVRx. They will receive education and hands-on experience with the VR headset to ensure safe and comfortable device use at home. Access to technical support will also be provided. Each week, participants will be asked to complete 7 assigned modules, averaging 5 minutes in duration and ranging from 2 to 16 minutes in

Protocol Title: Home-Based Intervention for Chronic Pain in Adults with Sickle Cell Disease (HIPAS)

duration, for a total of 56 modules across the program. The order of the modules is fixed but participants can repeat modules as desired. Participants in the control group will be asked to use the audio only version of EaseVRx, which excludes references to visual content, to complete 7 sessions weekly. They will receive an electronic link to the recordings on SoundCloud (a music streaming platform) where they can choose to stream or download the audio recordings on their smartphone, laptop, or desktop computer.

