2. Other exclusions: Medical instability as determined by healthcare providers at the study site; significant motor impairment; surgery within the last three months; planning to start a new pain management strategy (such as medication, physiotherapy, acupuncture, or cognitive behavioral therapy) in the next three months; history of major psychiatric disorder (such as schizophrenia or bipolar disorder) not controlled with medication or behavioral factors that would interfere with study procedures; alcohol or substance dependence, heart conditions, or the presence of implanted medical devices (such as cardiac pacemakers) as noted in the electronic health record; cognitive or developmental disabilities; active suicidal ideation; inability to read, write, or understand English; pregnancy; and/or plans for vacation in the next three months.

This study will not include any of these special populations:

- Adults unable to consent
- Individuals who are not yet adults (infants, children, teenagers)
- Pregnant women
- Prisoners

Community Participation

Adults with SCD are the target community for this study. Our preliminary and ongoing studies have been aimed at evaluating the chronic pain experience among adults with SCD and assessing their needs, goals, and preferences for future intervention studies such as this study. Therefore, the needs, goals, and preferences of adults with SCD have been incorporated in the design of this study of adults with SCD. De-identified study findings may be posted on the project website. This can provide a forum for obtaining feedback from the SCD community, which includes research participants and their family members or caregivers, healthcare providers, and visitors such as professionals and non-professionals. In addition, dissemination of results from this study will occur via publications and presentations to the SCD community at national and international professional conferences. Electronic copies of publications arising from the proposed study will be deposited in PubMed Central with proper tagging of data to ensure online discoverability and accessibility.

11. Vulnerable Populations

Not applicable

12. Local Number of Participants

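### Section 15 bars nursing women from VR but Section 10 does not exclude them, so an enrolled nursing woman could have her arm set by status or VR withheld after allocation

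*Combined protocol and SAP*

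**What the plan says.** - **Section 15, Procedures to Reduce Risks**, on exposure: "women who are pregnant or nursing a child will not participate in exposure to VR".
- **Section 10, Exclusion Criteria**: the list ends with "pregnancy; and/or plans for vacation in the next three months". The separate list of special populations that the study leaves out has "Pregnant women". Nursing appears in neither list, and no other criterion covers it.
- **Section 6, Procedures for Participants**: after baseline, "participants will be randomized 1:1 to receive either EaseVRx or control". The next sentence reads "Only individuals meeting the eligibility criteria for VR will be assigned to the VR group".
- **Section 15**, on candidates who answer yes on the cybersickness screen: "they will not be considered eligible for participating in the VR group only".
- **Section 15**, on pregnancy that begins during the study: "In that case, they will not be exposed to VR but may continue with other remaining study activities". There is no matching sentence for nursing.
- **Section 18, Data Analysis**: all outcomes are compared between the arms by intent-to-treat.

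**The concern.** Nursing status is known before randomisation. Section 10 lets a nursing woman in, and Section 15 keeps her from one of the two treatments. Two things can then happen, and the plan does not choose between them.

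1. She is placed in audio under the Section 6 rule. Her chance of VR is zero, and anyone who knows her status knows her arm. The audio arm then holds people of a kind that the VR arm cannot hold.
2. She is randomised and may draw VR, which is then withheld. Allocation stays random, but under intent-to-treat an unexposed person counts as VR. The Section 4 feasibility counts (module completion, engagement) would also record non-use that the protocol itself imposed.

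Identification is a further gap. Table 1 in Section 6 names a cybersickness screen but no step that asks about nursing. The attached forms are not part of the documents and may ask about it.

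**Working it through.** **The plan's own figure, as a yardstick.** The revision history gives a minimum detectable Cohen's d of 0.9 for 40 completers (20 per arm) at 80% power and a 5% level. Power at d = 0.9 with 20 per arm is 0.792 by the two-sample t-test and 0.812 by the normal approximation, so the figure reproduces. The present point does not depend on it.

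**The sections side by side.**

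| Question | Pregnant at entry | Nursing at entry | Positive cybersickness screen |
|---|---|---|---|
| Kept out of the study (Section 10)? | Yes | Not mentioned | Yes, as susceptibility |
| Barred from VR (Section 15)? | Yes | Yes | Yes, VR group only |
| Allocation and analysis if enrolled? | Not applicable | Not stated | Not stated |

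Only the pregnancy column is complete and consistent.

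**How many people.** Enrolment of 70 to 90 is from Sections 6 and 12. The share of women, 61%, is borrowed from the two earlier samples in Section 3 (61.2% of 103; 61.1% of 18). The share of women nursing at entry is not in the documents; 2-5% is an assumption.

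- Low: 70 × 0.61 × 0.02 = 0.9
- High: 90 × 0.61 × 0.05 = 2.7
- As a proportion p of participants: 0.61 × 0.02 = 1.22% to 0.61 × 0.05 = 3.05%
- Among 40 completers: 40 × 0.0122 = 0.5 to 40 × 0.0305 = 1.2

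**Branch 1, placed in audio, the rest randomised 1:1.** The audio arm is (1 − p)/2 + p = (1 + p)/2 of the total, so nursing women make up 2p/(1 + p) of it.

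- Low: 0.0244/1.0122 = 2.4%
- High: 0.061/1.0305 = 5.9%

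If these women differ from the others by 0.5 SD on the outcome (an assumption, direction unknown), the contrast between arms shifts by 0.5 × 0.024 = 0.01 SD to 0.5 × 0.059 = 0.03 SD. Power is not the cost here: with one such woman among 40 (19.5 against 20.5 on average) it remains 0.792.

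**Branch 2, randomised, VR withheld.** On average a proportion p of the VR arm is unexposed. If those women do as audio participants do, d = 0.9 becomes 0.9 × (1 − p).

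- Low: 0.9 × 0.9878 = 0.889
- High: 0.9 × 0.9695 = 0.873

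For one such woman among 40, half of one expected in VR, d = 0.9 × (1 − 0.5/20) = 0.877 and power is 0.772 against 0.792.

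**The case against.** The strongest reply is that Section 15 only restates the entry exclusions loosely. Its sentence takes pregnant and nursing women together, pregnant women are excluded at entry, and nursing may simply have been left off the Section 10 list. The documents do not rule this out, but the wording is against it. The sentence limits exposure to VR, not participation, and the same paragraph lets a woman who becomes pregnant stay in the study without VR. The Section 6 assignment rule and the cybersickness route both presuppose enrolled people who may not have VR. Even if it is an omission, the lists still have to be made to agree.

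Three further replies stand in full.

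- No section says that nursing women are given audio. That is inferred from the Section 15 bar together with the Section 6 rule.
- A reader might infer that the randomisation is broken or that the arms differ by design. The documents do not support that. Under branch 2 allocation stays random. Under branch 1 only the women concerned are affected.
- A reader might also infer that one section allows an exposure that another forbids. None does: Section 15 bars VR outright and Section 10 is silent. The safety side is limited to the absence of a listed step that would find these women.

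The numbers are soft too. The nursing rate has no source in the documents, and the 61% comes from other samples, one of them aged 18-30 only.

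**Conclusion.** The inconsistency is real and minor. Sections 10 and 15 differ on nursing women, and Section 6 turns that difference into an arm set by status for anyone barred from VR but enrolled. If such women are randomised instead, the result is an unexposed person counted as VR.

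On the stated assumptions, 1 to 3 of 70 to 90 participants are affected. The between-arm contrast would shift by 0.01 to 0.03 SD, or d would fall from 0.9 to between 0.87 and 0.89. Neither would change what this pilot can conclude. The point is worth acting on because the allocation and analysis of these participants are undefined and the repair is cheap. The cybersickness route has the same defect and is stated outright: Section 15 bars such people from the VR group only, while Section 10 excludes that susceptibility from the whole study.

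**What to change.** 1. Reconcile Sections 6, 10 and 15 so that one list of conditions barring VR exposure applies to every candidate at screening, before randomisation. Which clinical rule applies to nursing women is for the investigators to settle.
2. State in Section 6 that only people who could receive either arm are randomised, and in Section 18 that only they enter the between-arm comparison. Cover the cybersickness route in the same edit.
3. Add to the screening form a question for each condition on the reconciled list, if it is not already there.
4. The revision history for version 9 reports an observed drop-out rate, so people were already enrolled by then. Identify anyone enrolled while barred from VR, using baseline status in both arms alike, and run a sensitivity analysis without them. Removing only those who drew VR would itself unbalance the arms.

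The cost is a few sentences in one amendment, at most a few added questions on the screening form, a check of the baseline records and one extra model run.
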